6.2.2 Follow-up procedures

Follow-up assessments will be conducted 7 to 10 days after discharge from Visit 2 and will include recording of weight, a full physical examination, vital signs (supine blood pressure and pulse rate), blood sampling for routine hematology and clinical chemistry, urine sampling for routine urinalysis, 12-lead ECG, recording of concomitant medication, and recording of AEs and SAEs.

6.3 Safety

The principal investigator is responsible for ensuring that all personnel involved in the study is familiar with the content of this section.

6.3.1 Definition of adverse events

An AE is the development of an undesirable medical condition or the deterioration of a pre-existing medical condition following or during exposure to a pharmaceutical product, whether or not considered causally related to the product. An undesirable medical condition can be symptoms (eg, nausea, chest pain), signs (eg, tachycardia, enlarged liver) or the abnormal results of an investigation (eg, laboratory findings, ECG). In clinical studies, an AE can include an undesirable medical condition occurring at any time, including run-in or washout periods, even if no investigational product has been administered.

The term AE is used to include both serious and non-serious AEs.

6.3.2 Definitions of serious adverse event

An SAE occurring during any study phase (ie, run-in, treatment, washout, follow-up), that fulfills one or more of the following criteria:

- Results in death.
- Is immediately life-threatening.
- Requires in-patient hospitalization or prolongation of existing hospitalization.
- Results in persistent or significant disability/incapacity or substantial disruption of the ability to conduct normal life functions.

- Is a congenital abnormality or birth defect.
- Is an important medical event that may jeopardize the volunteer or may require medical intervention to prevent one of the outcomes listed above.

For further guidance on the definition of a SAE, see [Appendix B](#).

6.3.3 Recording of adverse events

Time period for collection of adverse events

Adverse events will be collected from the time of signature of the informed consent, throughout the treatment period and including the follow-up visit.

Serious AEs will be recorded from the time of informed consent.

Follow-up of unresolved AEs

Any AEs that are unresolved at the healthy volunteer's last AE assessment in the study are followed up by the investigator for as long as medically indicated, but without further recording in the eCRF. AstraZeneca retains the right to request additional information for any healthy volunteers with ongoing AE(s)/SAE(s) at the end of the study, if judged necessary.

Variables

The following variables will be collect for each AE;

- AE (verbatim).
- The date and time when the AE started and stopped.
- Maximum intensity.
 - Mild (awareness of sign or symptom, but easily tolerated).
 - Moderate (discomfort sufficient to cause interference with normal activities).
 - Severe (incapacitating, with inability to perform normal activities).
- Whether the AE is serious or not.
- Investigator causality rating against the investigational product (yes or no).
- Action taken with regard to investigational product.
- AE caused healthy volunteer's withdrawal from study (yes or no).
- Outcome.

In addition, the following variables will be collected for SAEs:

- Date AE met criteria for serious AE.
- Date Investigator became aware of SAE.
- AE is serious due to.
- Date of hospitalization.
- Date of discharge.
- Probable cause of death.
- Date of death.
- Autopsy performed.
- Causality assessment in relation to study procedure(s).
- Causality assessment in relation to other medication.
- Description of AE.

It is important to distinguish between serious and severe AEs. Severity is a measure of intensity whereas seriousness is defined by the criteria in Section 6.3.2. An AE of severe intensity need not necessarily be considered serious. For example, nausea that persists for several hours may be considered severe nausea, but not a SAE. On the other hand, a stroke that results in only a limited degree of disability may be considered a mild stroke but would be a SAE.

Causality collection

The investigator will assess causal relationship between investigational product and each AE, and answer ‘yes’ or ‘no’ to the question ‘Do you consider that there is a reasonable possibility that the event may have been caused by the investigational product?’

For SAEs causal relationship will also be assessed for other medication and study procedures. Note that for SAEs that could be associated with any study procedure the causal relationship is implied as ‘yes’.

A guide to the interpretation of the causality question is found in [Appendix B](#).

Adverse Events based on signs and symptoms

All AEs spontaneously reported by the healthy volunteer or reported in response to the open question from the study personnel: ‘Have you had any health problems since the previous visit/you were last asked?’, or revealed by observation will be collected and recorded in the

eCRF. When collecting AEs, the recording of diagnoses is preferred (when possible) to recording a list of signs and symptoms. However, if a diagnosis is known and there are other signs or symptoms that are not generally part of the diagnosis, the diagnosis and each sign or symptom will be recorded separately.

Adverse Events based on examinations and tests

The results from protocol-mandated safety assessments will be summarized in the clinical study report (CSR). Deterioration as compared to baseline in protocol-mandated safety assessments should therefore only be reported as AEs if they fulfill any of the SAE criteria or are the reason for discontinuation of treatment with the investigational product.

If deterioration in a laboratory value/vital sign is associated with clinical signs and symptoms, the sign or symptom will be reported as an AE and the associated laboratory result/vital sign will be considered as additional information. Wherever possible the reporting investigator uses the clinical, rather than the laboratory term (eg, anemia versus low hemoglobin value). In the absence of clinical signs or symptoms, clinically relevant deteriorations in non-mandated parameters should be reported as AE(s).

Any new or aggravated clinically relevant abnormal medical finding at a physical examination as compared with the baseline assessment will be reported as an AE.

NB. Cases where a volunteer shows an AST **or** ALT ≥ 3 x upper limit of normal (ULN) **or** total bilirubin ≥ 2 x ULN may need to be reported as SAEs, please refer to [Appendix D](#) 'Actions required in cases of combined increase of aminotransferase and total bilirubin – Hy's Law', for further instructions.

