Healthy male and female (of non-childbearing potential) volunteers aged 18 to 45 years (inclusive) who are non-smokers, have a body mass index (BMI) between 18 and 30 kg/m² (inclusive) and weigh at least 50 kg and no more than 100 kg (inclusive), have a calculated creatinine clearance greater than 50 mL/min using the Cockcroft-Gault formula. Healthy volunteers with current or past history of central serous retinopathy or retinal vein thrombosis, intra-ocular pressure greater than 21 mmHg or uncontrolled glaucoma will be excluded.

Investigational product, dosage and mode of administration

A single administration of 75 mg selumetinib will be administered as 3 x 25 mg oral capsules (Treatment A).

Comparator, dosage and mode of administration

Healthy volunteers will receive single daily oral doses of 600 mg (2 x 300 mg) rifampicin on Days 4 to 11 and Days 13 to 14 (Treatment B). On Day 12, the volunteers will receive 600 mg (2 x 300 mg) rifampicin and 75 mg (3 x 25 mg) selumetinib at the same time (Treatment C).

Duration of treatment

Volunteers will participate in the study for approximately 8 weeks; including screening over 28 days. Volunteers will be resident in the study center from Day -1 until all study assessments are completed on Day 15, with a follow-up visit 7 to 10 days after discharge (Day 15).

Outcome variable(s):

- Pharmacokinetics

The primary PK parameters will be: maximum observed plasma concentration (C_{max}), area under the plasma concentration-time curve from time zero to infinity (AUC), and area under plasma concentration-time curve to time of last measurable concentration ($AUC_{(0-t)}$).

The secondary PK parameters will be: time to reach maximum observed concentration administration (t_{max}), area under the plasma concentration time curve from zero to 12 hours post-dose ($AUC_{(0-12)}$), terminal rate constant (λ_z), terminal elimination half-life ($t_{1/2}$), apparent oral clearance (CL/F), apparent volume of distribution at steady state (V_{ss}/F), apparent volume of distribution during the terminal phase (V_z/F), and mean residence time (MRT) for selumetinib, and AUC, C_{max} , t_{max} , $t_{1/2}$, λ_z , AUC_{0-12} , $AUC_{(0-t)}$, and the metabolite to parent AUC and C_{max} ratios (MR_{AUC} and $MR_{C_{max}}$) for N-desmethyl selumetinib.

Pharmacokinetic parameters will not be determined for rifampicin. Only the 2 hours post-dose plasma concentrations will be reported.

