5.4 Blinding and procedures for unblinding the study (Not applicable)

5.5 Treatments

5.5.1 Identity of investigational product(s)

Table 3 Identity of the investigational product

Investigational product	Dosage form and strength	Manufacturer
Selumetinib	25 mg blue oral capsules (containing 25 mg free base equivalent of selumetinib Hyd-Sulfate)	

Selumetinib capsules will be packaged in high-density polyethylene (HDPE) bottles containing 60 capsules per bottle.

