12. STATISTICAL METHODS AND SAMPLE SIZE DETERMINATION

12.1 Description of analysis sets

12.1.1 Safety analysis set

All healthy volunteers who received at least 1 administration of investigational product (selumetinib or rifampicin) will be included in the safety population.

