12.2.2 Safety and tolerability

All safety data (scheduled and unscheduled) will be presented in the data listings. Continuous variables will be summarized using descriptive statistics (n, mean, SD, minimum, median, maximum) by treatment. Categorical variables will be summarized in frequency tables (frequency and proportion) by treatment.

Safety variables (eg, clinical laboratory values and vital signs) will be reported to the same precision as the source data. Derived variables will be reported using similar precision to those from which they were derived.

Extra measurements (such as unscheduled or repeat assessments) will not be included in the descriptive statistics by scheduled time point, but will be included in data listings. All AEs and clinical laboratory outliers that occur following the first dose of investigational product will be included in the analyses of AEs and outlier events, including episodes that occur at unscheduled evaluations, evaluations, or during the washout period.

All available data from healthy volunteers in the safety analysis set will be included in the safety analyses.

All AEs will be collected for each healthy volunteer from Day -1 Visit 2 until the follow-up visit. All SAEs will be collected for each healthy volunteer from the time when informed consent is obtained until the follow-up visit.

Adverse events will be listed for all healthy volunteers with AEs that occur before investigational product administration indicated on the listing. The number of AEs experienced following administration of the investigational product will be summarized in tables using the Medical Dictionary for Regulatory Activities (MedDRA) (Version 13.0 or higher) System Organ Class and Preferred Term. These summary tables will also be produced with severity and causality of AEs added as additional classification factors. The number of AEs overall, SAEs, OAEs, AEs that lead to withdrawal, AEs of severe intensity, and causally-related AEs will be summarized. Any AE occurring post-dose will be considered associated with the last administration of investigational product taken. Any AE occurring on Visit 2 Day -1 will not be included in the summaries.

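### One causality rating per AE against an 'investigational product' with two meanings leaves the related-AE counts after the first rifampicin dose dependent on how the term is read

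*Protocol*

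**What the plan says.** Section 6.3.3 lists the variables collected for every AE. The causality variable is "Investigator causality rating against the investigational product (yes or no". The investigator is asked: "Do you consider that there is a reasonable possibility that the event may have been caused by the investigational product". No drug is named. A further rating exists for serious events only: "For SAEs causal relationship will also be assessed for other medication and study procedures".

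The term is not defined in the abbreviations list, and its use varies.

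- **Selumetinib only.** The synopsis entry for investigational product reads "A single administration of 75 mg selumetinib will be administered as 3 x 25 mg oral capsules (Treatment A", and rifampicin appears under the separate heading "Comparator, dosage and mode of administration". In Section 5.5.1, "Table 3 Identity of the investigational product" has a single row, selumetinib.
- **Either drug.** Section 12.1.1 states: "All healthy volunteers who received at least 1 administration of investigational product (selumetinib or rifampicin) will be included in the safety population". Section 5.5.3 is headed as an additional study drug, yet its table places rifampicin in an investigational product column. The fluid restriction for Treatment B in Section 5.5.2 also applies the term to rifampicin.

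Section 12.2.2 adds causality as a classification factor in the AE tables and says "AEs of severe intensity, and causally-related AEs will be summarized". It also links each post-dose AE to the most recent dose of investigational product.

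**The concern.** The safety objective in Section 2.2 concerns selumetinib, and the related-AE tables are one of the outputs that serve it. For most of the study rifampicin has been given too, and the expected reactions overlap. Sections 1.3.3 and 1.3.4 list diarrhea, nausea, vomiting, rash and raised transaminases for both drugs.

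Take a non-serious rash on Day 8 that the investigator attributes to rifampicin. If the term means selumetinib, the answer is no. If it means either drug, the answer is yes. The volunteer, the event and the judgement are the same, but the related-AE table differs.

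This is a question of data collection. An analysis plan can define the tables, but it cannot recover a per-drug judgement that was never requested.

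**Working it through.** The plan gives no figure to reproduce here. The check sets the two meanings against the dosing schedule in Section 3.1.

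**Inputs.** Selumetinib is given on Days 1 and 12. Rifampicin is given on Days 4 to 14, which is 14 − 4 + 1 = 11 daily doses. Follow-up is 7 to 10 days after discharge on Day 15, so Day 22 to Day 25.

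**What a yes means, by onset of the event**

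| Onset | Narrow meaning (selumetinib) | Broad meaning (either drug) |
|---|---|---|
| Day 1 dose to first rifampicin dose, Day 4 | Selumetinib | Selumetinib, the only drug given so far |
| First rifampicin dose to Day 12 co-dose | Selumetinib; rifampicin unrated if non-serious | Either drug; timing helps the reader, but the rating names neither |
| Day 12 co-dose to follow-up | Selumetinib; rifampicin unrated if non-serious | One or both drugs, not separable |

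**Length of the unaffected window**

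- First dose to follow-up: 22 − 1 = 21 days to 25 − 1 = 24 days.
- Selumetinib only: 4 − 1 = 3 days, so 3/24 = 12.5% to 3/21 = 14.3%.
- Remainder: 18/21 = 85.7% to 21/24 = 87.5%.

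These are shares of time. The protocol gives no AE rates by period, so they are not shares of events.

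**Serious events.** The additional rating for other medication captures rifampicin if the narrow meaning holds. If rifampicin is itself investigational product, that item does not separate it from selumetinib.

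**Allocation to treatment.** The last-administration rule in Section 12.2.2 rests on the same term. Under the broad meaning, an event between the first rifampicin dose and the Day 12 co-dose belongs to a rifampicin dose, hence Treatment B. Under the narrow meaning, it goes back to the Day 1 dose, hence Treatment A. Separately, the synopsis comparator entry puts rifampicin on Days 13 and 14 under Treatment B, while Sections 3.1 and 5.5.2 describe it under Treatment C. Tabulation by treatment is therefore not a fully independent safeguard until the term is fixed, although recorded onset date and time would allow events to be re-sorted.

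**The case against.** The strongest reply is that the question works as written if the term means selumetinib, as Table 3 and the synopsis have it. It then asks about the drug named in the safety objective, on every day including Day 12. All that is lost is a rifampicin rating for non-serious events, which no objective requests. This is correct under that reading. It does not settle the matter, because Section 12.1.1 states the other meaning outright and nothing in Section 6.3.3 chooses between them.

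Second, design and tabulation already help. AEs are summarized by treatment, onset times are recorded, Treatment A precedes any rifampicin, and a Day 8 event falls in a rifampicin-only dosing period. This stands in large part. It limits the truly inseparable overlap to the period from the Day 12 co-dose onward, subject to the allocation problem shown above.

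Third, the eCRF and its instructions are not at hand and may name the drugs. That is possible, but it would not remove the contradiction in the protocol.

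Fourth, paired ratings on Day 12 may often be yes for both. That is a fair limit on the gain.

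A reader might infer that the trial cannot show what selumetinib caused, or that related-AE counts are wrong on the 10 of 12 dosing days when rifampicin is given alone. The documents support neither. Events rated yes before the first rifampicin dose point to selumetinib under both meanings, the narrow meaning yields a selumetinib rating throughout, and a count of dosing days does not measure affected events.

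**Conclusion.** The point holds with limited scope. The protocol uses one term in two senses and rests its only causality rating for non-serious AEs on that term. Related-AE counts are therefore ambiguous for events starting after the first rifampicin dose and for any count pooled over treatments. The number of events affected cannot be stated from the document.

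No AE disappears: all post-dose AEs are tabulated by System Organ Class and Preferred Term, and only the related flag changes. The primary PK comparison does not use the rating. The issue touches one descriptive output under a secondary objective, in a study of about 24 volunteers with no powered hypothesis test.

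The conclusion assumes that the form follows Section 6.3.3 as written. It is worth correcting because the change is cheap beforehand and the missing judgement cannot be derived afterwards.

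**What to change.** 1. Choose one definition of investigational product and use it in the synopsis, Sections 5.5.1, 5.5.3 and 12.1.1, and in the last-administration rule of Section 12.2.2. Reconcile the treatment label for rifampicin on Days 13 and 14 at the same time, since that rule depends on it.
2. In Section 6.3.3 and the eCRF, record two yes/no ratings for every AE, serious or not: reasonable possibility of causation by selumetinib, and the same for rifampicin.
3. In Section 12.2.2, tabulate causally related AEs per drug within treatment.

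The cost is one extra field per AE and one extra table column. Some events after the Day 12 co-administration may still be rated yes for both drugs, but the table would then show that the investigator could not separate them. No dose, schedule or clinical rule changes.

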6.3.4 Reporting of serious adverse events

All SAEs have to be reported, whether or not considered causally related to the investigational product, or to the study procedure(s). All SAEs will be recorded in the eCRF.

If any SAE occurs in the course of the study, then investigators or other study center personnel inform appropriate AstraZeneca representatives immediately, or **no later than 24 hours** of when he or she becomes aware of it.

The designated AstraZeneca representative works with the investigator to ensure that all the necessary information is provided to the AstraZeneca Patient Safety data entry site **within 1 calendar day** of initial receipt for fatal and life-threatening events **and within 5 calendar days** of initial receipt for all other SAEs.

For fatal or life-threatening AEs where important or relevant information is missing, active follow-up is undertaken immediately. Investigators or other study center personnel inform AstraZeneca representatives of any follow-up information on a previously reported SAE immediately, or **no later than 24 hours** of when he or she becomes aware of it.

6.3.5 Laboratory safety assessment

Blood and urine samples for determination of clinical chemistry, hematology, and urinalysis will be collected at the times indicated in Table 2. The urine drugs of abuse screen as well as the alcohol screen will be performed by the laboratory at the study center and all other samples, including the cotinine screen, will be analyzed by the . The date and time of sample collection will be recorded in the eCRF.

The laboratory variables to be measured are provided in Table 4.

Table 4 Safety laboratory variables

Hematology (blood)	Clinical chemistry (serum)	Urinalysis (urine)
Platelet count	Creatinine	Erythrocytes
Leukocyte differential count ^a	Bilirubin total	Albumin
Leukocytes count	Alkaline phosphatase (ALP)	Glucose
Hemoglobin	Alanine aminotransferase (ALT)	
Erythrocyte volume fraction	Aspartate aminotransferase (AST)	
Reticulocytes	Albumin	
Erythrocytes	Calcium total	
Erythrocyte mean cellular volume	Sodium	
	Potassium	
	C-reactive protein	
	Thyroxine free ^a	
	Thyroid stimulating hormone ^a	
	Follicle-stimulating hormone ^b	

^a These tests should be performed at screening only.

^b Follicle-stimulating hormone will be tested only at screening and only for post-menopausal females.

At screening a blood sample will be collected to screen for hepatitis B, C, and HIV. Creatinine clearance will be calculated at screening using the Cockcroft-Gault formula:

$$\text{Estimated CrCL (mL/min)} = \frac{(140 - \text{age [years]}) \times (\text{body weight [kg]}) \times (0.85)^a}{\text{Serum creatinine (mg/dL)} \times 72}$$

^a For females.

A urine sample will be collected at screening and Day -1 of Visit 2 to screen for the following drugs of abuse: amphetamines, barbiturates, benzodiazepines, cocaine, marijuana, methadone, methamphetamine, ecstasy, opiates, phencyclidine, oxycodone, and tricyclic antidepressants.

Alcohol breathalyzer test and urine cotinine test will be performed at screening and Day -1 of Visit 2.

Additional and repeat testing may be performed at the discretion of the investigator. Laboratory values outside the reference limit suspected to be of any clinical significance will be repeated. Healthy volunteers in whom suspected clinical significance is confirmed will either not be included or if already enrolled will be followed until normalization or for as long as the investigator considers necessary.

In case a volunteer shows an AST **or** ALT ≥ 3 x ULN **or** total bilirubin ≥ 2 x ULN please refer to [Appendix D](#) ‘Actions required in cases of combined increase of aminotransferase and total bilirubin – Hy’s Law’, for further instructions.

For blood volume see Section [7.1](#).

